Evaluating the use of sublingual sufentanil in patients with suboxone treatment who are undergoing ambulatory surgery- a case series

Introduction

Despite widespread public awareness programs and pain management recommendations, opioid use disorder (OUD) remains a significant medical challenge¹. Opioid use disorder is a chronic replacing illness with considerable mortality and morbidity.² One of the long term management programs to avoid opioid use relapse is to include an opioid agonist (methadone or buprenorphine) in the management regime.^{3, 4} According to the recent publication, the number of Medicaid-covered prescriptions for buprenorphine increased almost fivefold nationally — to 6.2 million from 1.3 million — between 2011 and 2018.⁵

Although studies have reported socioeconomic disparities in receiving treatment between Methodone and buprenorphine, Montefiore Medical Center has played a pivotal role in providing buprenorphine treatments to its low-income patients since the FDA approval.⁶ According to the audit, there are currently well over 1000 patients in the system on Suboxone, and thousands more in the community receive Suboxone from private practice practitioners.

The treatment of acute pain, especially postoperative pain in patients taking buprenorphine, is particularly challenging.^{4, 7} The high receptor binding affinity, the long half-life, and partial agonism of buprenorphine may inhibit the analgesic actions of traditional opioids, hence the potential for uncontrolled postoperative pain and serious adverse events.^{7, 8}

To fulfill targeted medical needs in 2018, the FDA has approved sublingual sufentanil (DSUVIA), an opioid analgesic.⁹ DSUVIA is indicated for the management of acute pain severe enough to require an opioid analgesic and for which alternative treatments are inadequate.⁹ DSUVIA is restricted to use in certified medically-supervised health care settings – such as hospitals, surgical centers, and emergency departments – for administration by a health care professional.⁹ Dsuvia has previously approved by the European Medicines Agency in July under the brand name Dzuveo.

In the era of an opioid crisis, especially the number of surgeries performed is increasing, and patients who are on maintenance therapy for opioid disorders need more robust strategies for their postoperative pain management. Current postoperative pain management has several limitations. Intravenous morphine has a delayed half-life and a higher propensity for opioid-induced adverse events.¹⁰ Even though hydromorphone has a quicker onset of action compared to morphine, the adverse event profiles are similar, and some studies suggesting a higher rate of sedation and CNS related adverse events.^{11, 12} The lipophilic nature of fentanyl results in a quick onset of action but prompting supplemental doses for adequate pain relief. Similarly, other lipophilic opioids such as sufentanil, alfentanil, and remifentanil, can have an even more abrupt offset of analgesia due to brief initial distribution phases and/or rapid metabolism following IV bolus administration, and are therefore rarely used for postoperative analgesia.¹¹

Sufentanil has a high affinity and potency at the mu-opioid receptor, making this an ideal drug of choice for patients on Suboxone. The highly lipophilic nature of sufentanil allows for prompt uptake from the sublingual tissues and cross the blood brain barrier in a relatively shorter period of time, a 6.2 minute

$t_{1/2ke0}$ compared to the 2.8 hours $t_{1/2ke0}$ of intravenous morphine.¹³ Additionally, the average interdosing interval of SST in this study was 185 minutes over 12 hours, suggesting that the administration's sublingual route results in an extended duration of analgesia compared with the IV bolus administration of lipophilic opioids, such as fentanyl or sufentanil.¹⁴ The time from peak plasma concentration (Cmax) to 50% of Cmax for sublingual sufentanil (2.5 hours) is extended 25-fold compared with bolus IV sufentanil administration of the same dose. Finally, unlike morphine and hydromorphone, sufentanil also avoids the issue of active metabolites that can lead to prolonged, untoward effects, which can complicate postoperative care and affect patient discharge.¹⁵

The safety and efficacy of sufentanil have been demonstrated in different types of surgeries. After hip or knee arthroplasty, patients who received sublingual sufentanil reported lesser postoperative pain compared to placebo.¹⁴ Similar results were reported by patients who had undergone open abdominal surgery.¹⁵ Additionally, in one of the recent publications, the use of sublingual sufentanil in the preoperative period resulted in reduced opioid usage in the post-operative period and shorter time in the postoperative anesthesia care unit.¹⁶

In this case, series, we are testing the hypothesis that sublingual sufentanil (Dsuvia) will improve postoperative pain management in the PACU in ambulatory surgery patients taking Suboxone.

Primary Endpoint – We will evaluate the total amount of morphine equivalence (MME) in the perioperative period (defined as combined total opioid used intra-op and in the PACU).

Secondary Endpoint(s) – We will evaluate the time to fit to discharge from the PACU, the need for additional opioids and time to take the first additional opioid within 24 hours after being discharged from the hospital, and finally, the adverse events in the intraoperative period , PACU and in the 24 hours after being discharged from the PACU (i.e., nausea, vomiting, itching, hypotension, dizziness.)

Methods

Study Design:

Prospective case series study.

Inclusion criteria

- Age range 18-100 years
- Currently taking Suboxone
- ASA physical score 1-3
- Able to provide a signed informed consent
- General anesthesia (either endotracheal intubation or laryngeal mask airway) or **MAC** (**monitored anesthesia care**) without the use of regional anesthesia

Exclusion criteria

- Known allergic reactions to Dsuvia and its excipients
- Severe respiratory illness including exacerbation of asthma attack
- Significant intraoperative hemodynamic instability
- Use of Regional anesthesia techniques

Informed Consent

According to the Montefiore standard of care, to prepare patients for surgery, the perioperative team contact patients within 1-3 days before the surgery. During this phone call, patients are given all the instructions regarding the surgical preparation, and the operative team makes sure all the needed medical records are in place. During this phone call, patients will be specifically asked about suboxone use, and an email will be sent to the research team to inform the details of the suboxone patients. The research team will screen the patients and those patients fulfilling the inclusion-exclusion criteria will be called on the day before surgery for their interest in participating in a research study. Interested patients will be provided with the study details, and all their questions will be answered. The signing of the consents will take place on the day of the surgery, an investigator associated with the study will be responsible for obtaining the informed consents.

In terms of surgery and anesthesia, the routine standard of care practiced in our hospital will be maintained for all the subjects enrolled in the study. During the study period, all the intraoperative and postoperative patient pain management guidelines will be standardized. According to the standard of practice in our institution, induction of anesthesia will take place. After induction of anesthesia, instead of intra-op and post-op Fentanyl 50mcg as needed, the patients will receive sublingual sufentanil (Dsuvia) intra-op and post-op. Detailed sublingual sufentanil is described in the next paragraph. Patients will be discharged home based on the discharge criteria followed at our institution. One of the research associates will call the patient 24 hours after discharge from the PACU to collect the information regarding their post-discharge opioid use, current pain score, adverse events, and information regarding the ED visits.

Study Objective Assessments

A research associate will be collecting the data prospectively and from the medical records. All the assessments will be coordinated with the standard of care administered at our hospital.

Study Medication and Storage

The sponsor of the study is responsible for providing the study medication. The patient or the insurance will not be billed for the study medication. Study medication will be stored in the research pharmacy at Hutch. All appropriate storage instructions will be followed, and the pharmacist will be responsible for the drug audit. On the day of surgery for an enrolled subject, research personnel will retrieve medication from the pharmacy and deliver it to the physician for administration to subjects.

Sublingual sufentanil (Dsuvia) Study Protocol Pain Medications:

Pre-op:

Acetaminophen 975mg PO

Intra-op for induction (doses as per standard):

IV Midazolam

IV Fentanyl

IV Lidocaine

IV Propofol

After induction and before incision

Ketamine .35-.5 mg/kg IV

Dsuvia 30mcg SL (1st dose)

Postop:

If pain < or = 4/10,

Give no additional medications

If pain > 4/10

give Dsuvia 30mcg SL (2nd dose)

if 30 minutes after Dsuvia 2nd dose & pain is >4/10

give Ibuprofen 800mg IV

if 60 minutes after Dsuvia 2nd dose & pain is >7/10

give hydromorphone 0.4 mg IV

Interim Analysis

We are planning to conduct an interim analysis to evaluate the use of a single dose of Dsuvia in the intraoperative period. For this purpose, if 8 of the first 15 patients require a second dose of Dsuvia in the PACU, then the protocol will be changed to give the 2nd dose of Dsuvia in the OR at 15 minutes (or more) before extubating (and more than 1 hour since the 1st dose). The rest of the protocol will stay the same.

Comparison group

The comparison group in this study will be randomly selected from a cohort of the patients satisfying inclusion and exclusion criteria. The time frame for the comparison group will be the first Dsuvia patient to the last Dsuvia patient. For the comparison group, all the data points will be collected retrospectively. For comparison, group data points after the discharge from the hospital will not be collected. We are requesting a waiver of consent and HIPAA authorization for the comparison group as this will be

conducted retrospectively. A waiver will be needed because subjects may not be possible due to reasons such as relocation, wrong contract information given, or are no longer being seen at our institution.

Statistical analysis

We are conducting this study as a pilot study. This pilot study's sample size is calculated based on the assumption that approximately 70% of the patients receive at least one dose of rescue opioid in the PACU. As this drug's efficacy in reducing the rescue opioids used in the PACU in this population is not studied previously, we plan to use a 50% rate reduction for calculating the sample size in this pilot study. According to our calculation estimate, we need to study 30 patients (alpha=0.05 and 1-Beta=0.85) in each group. The study will not be powered for secondary outcomes.

Descriptive statistics will be used to report all baseline demographic and clinical characteristics such as (age, gender, type of surgery, medications, ASA status, comorbidities). The primary endpoint amount of opioids used in the perioperative period will be compared using Wilcoxon rank-sum tests, and categorical variables such as adverse events and the number of patients requiring additional opioids will be analyzed using chi-square analysis or Fisher's exact tests. All the analysis will be two-tailed, and a p-value of <0.05 is considered statistically significant.

Data Management

All study data will be collected and entered into the computer database. Each subject will be assigned to a random number code, and the key linking the code and the subject identifier will be stored in a locked cabinet. The computer database will be password protected and will be kept on the HIPAA compliant Montefiore drive. The research manager is responsible for auditing the consistency of the data transcribed from the paper CRF to the computer. A protocol violation log will be maintained, and all protocol violations will be reported to the IRB and DSMB. The planned interim analysis (halfway through the recruitment) will be mainly focused on the additional dose of opioids in the PACU rather than the efficacy of the NMB reversal.

DSMB

The data safety monitoring board will be comprised of an anesthesiologist and a surgeon. All unanticipated serious adverse events will be reported to the DSMB. In the event of unanticipated serious adverse events, the continuation of the study will be at the discretion of DSMB and IRB. Periodic DSMB meetings will evaluate the occurrence of any study-related adverse events.

Human Safety

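### The 85% power belongs to a PACU rescue-opioid proportion, not to the primary MME total, and no sufentanil-to-morphine conversion is fixed for that total

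*Combined protocol and SAP*

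**What the plan says.** The Primary Endpoint paragraph defines the primary as the "total amount of morphine equivalence (MME) in the perioperative period (defined as combined total opioid used intra-op and in the PACU"). Under Statistical analysis, "The primary endpoint amount of opioids used in the perioperative period will be compared using Wilcoxon rank-sum tests".

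The sample-size paragraph of the same section starts from a different outcome, that "approximately 70% of the patients receive at least one dose of rescue opioid in the PACU". It applies a 50% rate reduction and concludes that "we need to study 30 patients (alpha=0.05 and 1-Beta=0.85) in each group". It adds that "The study will not be powered for secondary outcomes". The section closes with "All the analysis will be two-tailed, and a p-value of <0.05 is considered statistically significant".

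On what enters the total, the text under Informed Consent says that "instead of intra-op and post-op Fentanyl 50mcg as needed, the patients will receive sublingual sufentanil (Dsuvia) intra-op and post-op". The pain-medication schedule lists "Dsuvia 30mcg SL (1st dose") after induction and before incision, with no pain condition. A second dose in the PACU, and later hydromorphone, depend on the pain score. No section gives a morphine-equivalent factor for sufentanil, fentanyl or hydromorphone.

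**The concern.** There are two linked problems.

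- **The power statement is attached to the wrong outcome.** A PACU-only yes/no outcome was sized, while the primary is an amount summed over the operating room and the PACU. Because the plan disclaims power only for secondary outcomes, a reader will naturally take 85% as the power of the primary test. The sized proportion is not itself a listed endpoint: the need for additional opioids in the secondary list is tied to the 24 hours after discharge.
- **The primary cannot be computed as written.** Counting Dsuvia in the total is coherent, since it replaces as-needed fentanyl that is also counted. But every Dsuvia patient carries at least one converted sufentanil dose, while comparators carry fentanyl only as needed. The factor rescales one drug in one group, so a rank test does not remove its influence. If the factor is chosen after data are seen, that choice can decide whether the result reads as less opioid, no difference or more.

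**Working it through.** **1. The plan's own figure.** Inputs from Statistical analysis: 0.70 versus 0.35 (the 50% reduction read as relative), alpha 0.05, power 0.85, 30 per group. Mean proportion 0.525.

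Pooled normal formula, two-sided:

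n = [1.960·√(2·0.525·0.475) + 1.036·√(0.70·0.30 + 0.35·0.65)]² / 0.35² = 34.97, so 35 per group.

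One-sided, with 1.645 in place of 1.960: 27.85, so 28 per group.

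Two-sided power at 30 per group: Φ[(0.35·√30 − 1.960·0.706)/0.661] = Φ(0.806) = 0.790. One-sided it is 0.873.

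Exact binomial enumeration at two-sided 0.05:

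| n per group | Chi-square (uncorrected) | Fisher |
|---|---|---|
| 30 | 0.798 | 0.714 |
| 33 | 0.856 | 0.790 |
| 35 | 0.835 | 0.769 |
| 36 | 0.851 | 0.786 |
| 40 | 0.904 | 0.859 |

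Exact power does not rise smoothly. Chi-square passes 0.85 at 33, drops to 0.828 at 34, and is above 0.85 again from 36. So 30 per group at 85% is not reproduced under the two-tailed rule. It is close to a one-sided calculation.

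**2. What 30 per group can detect on the primary.** The plan gives no MME mean, SD or difference, so a required sample size cannot be derived. The detectable effect can. Noether's formula, total N = 60, equal groups, two-sided 0.05, power 0.85:

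(p − 0.5)² = (1.960 + 1.036)² / (12·0.25·60) = 8.978/180 = 0.0499, so p = 0.723.

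A normal-shift approximation with Wilcoxon efficiency 3/π gives d = 2.996·√(2/(30·0.955)) = 0.79 SD, or P = Φ(0.79/√2) = 0.71. On that scale, power at 30 per group is 47% for 0.5 SD, and 76 per group would be needed for 85%.

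**3. Influence of the conversion (illustration).** Every input here is an assumption except 30 per group and the 70% and 35% figures; applying 35% to the second Dsuvia dose is also an assumption. Let one 30-mcg Dsuvia dose count as r fentanyl 50-mcg doses. Comparators average k intra-op doses, and 70% of them have on average 2 PACU doses. Induction fentanyl is the same in both groups, and hydromorphone is ignored.

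Mean totals beyond induction: Dsuvia r + 0.35r = 1.35r; comparators k + 0.7·2 = k + 1.4. They are equal at r = (k + 1.4)/1.35, which is 1.78, 2.52 and 3.26 for k = 1, 2 and 3. Below that value the Dsuvia mean is lower; above it, higher.

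Simulation at k = 2, 4,000 trials per setting, two-sided Mann-Whitney, 30 per group, comparators Poisson(k) intra-op and 1 + Poisson(1) PACU doses in 70%:

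| r | Significantly lower on Dsuvia | Significantly higher on Dsuvia |
|---|---|---|
| 1.5 | 91% | 0% |
| 2.5 | 4% | 4% |
| 4 | 0% | 97% |

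These runs hold induction fentanyl constant. With independent normal variation in it, SD 1 dose, the 91% becomes about 79% and the 97% about 92%; with SD 2, about 51% and 75%. The flip remains.

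Only the yes/no second-dose rate is held fixed across rows. Mean PACU opioid on Dsuvia is 0.35r (0.53, 0.88, 1.40) against 1.40 in comparators. Leaving Dsuvia out of the total at k = 2 makes its group significantly lower in every simulated trial.

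**The case against.** The plan calls itself a pilot in an unstudied population and says openly what its sample size rests on, so nobody is misled about the calculation's input. That softens the consequence of limited power. It does not remove the mismatch, because the plan still states a power and a p<0.05 test of the primary.

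The sample-size sentence does not state sidedness, and a one-sided calculation gives 28 per group and 87% power at 30. That may explain the figure, but it conflicts with the two-tailed rule later in the same section.

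The simulation percentages depend on the assumptions. Induction fentanyl will vary, and the plan does not say whether a second Dsuvia dose counts as rescue. If the interim rule triggers and later patients receive both doses in the OR, a 15/15 split gives a mean of (1.35r + 2r)/2 = 1.675r, and break-even at k = 2 falls from 2.5 to 3.4/1.675 = 2.0. All of this stands. It changes the percentages and the crossing point, but not the finding that the direction depends on an unstated factor.

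Finally, a chi-square or Fisher test of the number needing additional opioids is already planned. What is missing is a definition of that outcome in the PACU.

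**Conclusion.** The concern holds and should be fixed. The stated 85% does not cover the primary MME comparison, for which 30 per group gives 85% power only at P(lower MME) of about 0.72. For the proportion that was sized, two-sided exact power is about 0.80 (chi-square) or 0.71 (Fisher). These figures rest on the plan's own inputs, the 50% reduction read as relative, and no dropout allowance, since none is stated.

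The missing conversion is a fact of the text. Its effect on the result is shown only under assumed opioid use, so the simulation demonstrates sensitivity and does not predict this trial's outcome.

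**What to change.** Keep MME as primary and amend as follows.

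1. State that the 85% figure does not apply to the primary, and give what 30 per group can detect: P(lower MME) of about 0.72 at 85% power, two-sided 0.05.
2. Correct the figure for 70% versus 35% with 30 per group to about 0.80 (chi-square) or 0.71 (Fisher).
3. Before analysis, fix one conversion table covering sufentanil, fentanyl and hydromorphone, with a sensitivity range for sufentanil. State that study Dsuvia counts in the total. Report intra-op MME, PACU MME and the total, with and without Dsuvia, noting that leaving it out favours the Dsuvia group almost automatically.
4. Define the proportion receiving any PACU opioid, second Dsuvia dose included, as a secondary endpoint with the chi-square or Fisher test already planned. Report it separately for patients treated before and after any interim change that moves the second dose into the OR; with about 15 patients in each part this is descriptive. Do not make it the primary unless the interim rule is reconciled with it. The trigger of 8 of 15 is met, in exactly this form or higher, with probability 0.11, 0.50 and 0.95 at true second-dose rates of 0.35, 0.50 and 0.70.

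The cost is amendment wording and a few summary rows. No new data are needed, since the primary already requires each patient's intra-op and PACU opioids. The price is a less favourable power statement and the possibility that the sensitivity range shows the conclusion changing with the conversion.

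### The adverse-event window opens before the first Dsuvia dose, so induction hypotension counted in both groups pulls the safety comparison towards no difference; induction fentanyl needs a separate report, not a new primary endpoint

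*Combined protocol and SAP*

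**What the plan says.** The Introduction sets the primary endpoint as total morphine equivalents over the perioperative period, "defined as combined total opioid used intra-op and in the PACU". The Secondary Endpoint(s) paragraph counts "the adverse events in the intraoperative period , PACU and in the 24 hours after being discharged from the PACU" and names hypotension among the events. Neither paragraph says when the intraoperative period begins.

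The best guide is the medication list under Sublingual sufentanil (Dsuvia) Study Protocol Pain Medications. Midazolam, fentanyl, lidocaine and propofol stand under "Intra-op for induction (doses as per standard", so the protocol itself files induction as intra-op. The first Dsuvia dose stands in the next block, "After induction and before incision". The Informed Consent section describes the contrast in the same order: "After induction of anesthesia, instead of intra-op and post-op Fentanyl 50mcg as needed, the patients will receive sublingual sufentanil (Dsuvia) intra-op and post-op".

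The Comparison group section says: "For the comparison group, all the data points will be collected retrospectively". Nothing after hospital discharge is collected for that group, so the two-group comparison of adverse events rests on the operating room and the PACU alone. The Statistical analysis section gives a rank-sum test for the primary and chi-square or Fisher tests for adverse events.

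**The concern.** Both windows open before the study drug is given. A tablet given after induction cannot cause hypotension that occurred during induction. Yet a patient who was hypotensive only at induction counts as having had the event. Once counted, that patient cannot add to any later difference between the groups, so a real post-dose excess on Dsuvia, or a real reduction, is reported as smaller than it is. In a pilot, whose estimates will be read more closely than its p-values, this pushes the safety message towards no difference.

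Induction fentanyl also enters the primary total. The protocol fixes no amount, pools general anesthesia with monitored anesthesia care, and leaves the choice to clinicians who know which patients will get Dsuvia. It can therefore add spread, or a group difference, that Dsuvia did not cause. The stated hypothesis is that Dsuvia "will improve postoperative pain management in the PACU in ambulatory surgery patients taking Suboxone", and the induction dose is not part of that.

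**Working it through.** The plan gives no figure for either window, so there is none to reproduce. The rates and SD ratios below are assumptions.

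**1. Adverse events.** Let p be the post-dose hypotension rate in a group and q the induction hypotension rate. Take q to be the same in both groups and independent of later events, and count each patient once.

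- Counted rate = 1 − (1 − q)(1 − p)
- Counted risk difference = (1 − q)(p_D − p_C), with D for Dsuvia and C for comparison

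With assumed p_C = 5%, p_D = 20% and 30 per group:

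| q | Comparison | Dsuvia | Risk difference (points) | Risk ratio | Exact Fisher power |
|---|---|---|---|---|---|
| 0 | 5.0% | 20.0% | 15.0 | 4.0 | 24% |
| 10% | 14.5% | 28.0% | 13.5 | 1.93 | 16% |
| 30% | 33.5% | 44.0% | 10.5 | 1.31 | 8% |
| 50% | 52.5% | 60.0% | 7.5 | 1.14 | 5% |

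For q = 30%: 1 − 0.7 × 0.95 = 33.5%, 1 − 0.7 × 0.80 = 44.0%, and 44.0/33.5 = 1.31.

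A second assumed pair, 10% v 30%, behaves the same way. At q = 10% and 30% the difference falls from 20 points to 18 and 14, and the ratio from 3.0 to 1.95 and 1.38.

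Without independence, the counted difference is 1 − q times the difference among patients who were not hypotensive at induction. If q differs between the groups, the result is bias in either direction: with no post-dose difference at all, the counted difference is (q_D − q_C)(1 − p).

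**2. Primary opioid total.** Write the total as induction plus post-induction opioid. Let r be the ratio of their SDs (induction over post-induction) and ρ their correlation. If induction opioid has the same distribution in both groups, the expected difference is unchanged, and the standardised difference is divided by √(1 + r² + 2ρr). A constant induction dose leaves the ranks unchanged (simulated Wilcoxon power 0.84, against 0.83 with no induction component, equal within simulation error).

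- With an assumed post-induction difference of 0.8 SD, 30 per group and ρ = 0, simulated Wilcoxon power is 0.83, 0.82, 0.75 and 0.56 at r = 0, 0.25, 0.5 and 1.0.
- From a 79% starting point, the noncentrality is 1.960 + 0.806 = 2.766. Dividing by 1.031, 1.118 and 1.414 (r = 0.25, 0.5, 1.0; ρ = 0) gives 2.683, 2.474 and 1.956, so power of 77%, 70% and 50%.
- With ρ = −0.3 and r = 0.5, the divisor is √0.95 = 0.975 and power is 81%, a slight gain.

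The 79% is the two-sided normal-approximation power of 30 per group for 70% v 35% with PACU rescue opioid, the inputs of the plan's sample size. It falls short of the stated 85%, which is a separate matter. That endpoint contains no induction opioid, so 79% serves here only as a starting value.

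**3. What a post-induction primary would miss.** Suppose clinicians give 50 mcg more fentanyl at induction to Dsuvia patients and 50 mcg less afterwards. The all-in fentanyl difference is +50 − 50 = 0. Counted from end of induction it is −50 mcg, an apparent benefit that is only a shift in timing.

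**The case against.** The strongest reply is that a combined perioperative total is a deliberate and legitimate endpoint. It measures exposure under the whole strategy, and step 3 shows that it protects against moving fentanyl into induction. That stands, and it is why the primary should not be replaced.

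A reader might also infer that the primary comparison has lost much of its power, down to 50% and an effective sample of 15 per group (30 ÷ 2 at r = 1.0). The documents do not support this. They give no SD for morphine equivalents, the 79% comes from a different endpoint, pain management is to be standardised, and the assumed range includes no loss or a small gain.

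On adverse events, several limits stand:

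- Of the named events, hypotension is the one mainly affected. Nausea, itching and dizziness are patient-reported, and vomiting at induction is unlikely.
- The exclusion for marked hemodynamic instability during surgery may remove severe cases. It has no threshold, so milder ones stay in the count.
- The Human Safety section puts Dsuvia's common adverse events, hypotension included, below 2%, well under the assumed 20%. At 2% v 5%, Fisher power is below 1% even without dilution.
- The plan claims no power for secondary outcomes, so a fall from 24% to 8% is no material loss.

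None of these removes the attenuation of the estimate, which follows for any q above zero under the assumptions in step 1.

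**Conclusion.** The point holds for adverse events, chiefly hypotension, and is minor. The counted risk difference is 1 − q times the post-dose difference. Under the assumed 5% v 20%, a fourfold excess would be reported as 1.9-, 1.3- or 1.1-fold at q = 10, 30 or 50%. The direction follows from the protocol's own order of events, given equal q in the groups; the size cannot be fixed from the documents. The reading also depends on induction falling within the intra-op period, which rests on the heading in the medication list.

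It would go too far to say that pre-dose hypotension is held against Dsuvia. Where induction rates are equal, it is counted equally in both groups and hides a difference without creating one. Nor is the primary endpoint wrongly defined. Induction fentanyl can add noise or a group difference, which justifies reporting it separately and adding a supportive analysis.

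**What to change.** In the Introduction's endpoint paragraphs:

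- Compare intraoperative adverse events from end of induction onward in both groups, and list earlier hypotension separately by group. End of induction is the workable common start, because comparison patients have no Dsuvia time.
- Keep the all-in total of morphine equivalents as the primary.

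In the Statistical analysis section:

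- Add a supportive Wilcoxon comparison of morphine equivalents from end of induction to PACU discharge.
- Report induction fentanyl by group.

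No treatment changes. The cost is that events and opioid doses must be sorted by time from the chart, retrospectively for the comparison group; the protocol does not say how finely its medical records are timed. End of induction is a proxy that slightly precedes the dose, and hypotension from induction drugs may run past it. For monitored anesthesia care, the plan must state the equivalent starting point once and apply it to both groups.

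### The PACU second Dsuvia dose has no minimum time since the first, although the plan's only dose-spacing condition is more than 1 hour

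*Combined protocol and SAP*

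**What the plan says.** The regimen is set out under Sublingual sufentanil (Dsuvia) Study Protocol Pain Medications. Dose 1 (30 mcg) is placed "After induction and before incision", together with ketamine and following induction with midazolam, fentanyl, lidocaine and propofol. In the Postop list, a score above 4/10 leads directly to "give Dsuvia 30mcg SL (2nd dose". Two later steps have clocks, ibuprofen at 30 minutes and hydromorphone at 60 minutes, but both run from dose 2; the hydromorphone line, for example, begins "if 60 minutes after Dsuvia 2nd dose & pain is >7/10".

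The Interim Analysis section contains the only spacing condition between Dsuvia doses. The trigger is "if 8 of the first 15 patients require a second dose of Dsuvia in the PACU". If it is met, the new instruction reads "give the 2nd dose of Dsuvia in the OR at 15 minutes (or more) before extubating (and more than 1 hour since the 1st dose", and everything else is left unchanged, so the PACU line gains no interval after a switch.

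The hypothesis concerns Dsuvia "in ambulatory surgery patients taking Suboxone". The inclusion criteria allow "General anesthesia (either endotracheal intubation or laryngeal mask airway) or" monitored anesthesia care (MAC). Neither the inclusion nor the exclusion criteria set a minimum length of surgery. The surgery and anesthesia paragraph under Informed Consent says that "all the intraoperative and postoperative patient pain management guidelines will be standardized".

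**The concern.** The same drug at the same dose is given as a second dose in two settings. In one the plan asks for more than an hour since dose 1; in the other it asks only for a pain score. The text does not say whether this difference is intended.

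What is at stake is opioid exposure in short cases. A PACU dose inside the hour would come on top of dose 1 and the induction fentanyl and midazolam and, in general-anesthesia cases, after the airway device is out. The Introduction reports that sublingual sufentanil takes 2.5 hours to fall from peak plasma concentration to half of it. On that figure, within the first hour dose 1 is either still rising towards its peak or not yet down to half of it. The plan says pain management will be standardized, yet the spacing of these two doses is left to whoever is in the PACU.

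**Working it through.** The plan states no figure to reproduce here. The check compares the two second-dose rules and then works through illustrative times.

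**The rules side by side**

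- Operating-room dose, only after an interim switch: no pain score needed; at least 15 minutes before extubation; more than 60 minutes since dose 1.
- PACU dose, in force from the first patient: pain above 4/10; no time since dose 1.
- Other candidates for a PACU interval: the 30- and 60-minute clocks start at dose 2 and govern other drugs. The 185-minute average interdosing interval in the Introduction describes a cited study. The remark under Human Safety about strict guidelines states no interval. None of these spaces dose 2 from dose 1 in this trial.

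**Illustrative timing**

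From the plan: the 60-minute operating-room floor, ibuprofen at dose 2 + 30 minutes, hydromorphone at dose 2 + 60 minutes. Assumed, because the plan gives no case lengths: S = 20 to 45 minutes from dose 1 to the end of the case, and R = 5 to 10 minutes from then to a PACU score above 4/10.

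- Time of dose 2 as written = S + R. Short of the hour by 60 − (S + R).
- Example, S = 30 and R = 10: dose 2 at 30 + 10 = 40 minutes; 60 − 40 = 20 minutes short.
- Shortest, S = 20 and R = 5: dose 2 at 25 minutes; 35 short.
- Longest, S = 45 and R = 10: dose 2 at 55 minutes; 5 short.
- If S + R exceeds 60 minutes, there is no shortfall and nothing changes.

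**What a 1-hour condition would cost these patients**

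- Dose 2 waits 5 to 35 minutes (20 in the example).
- Hydromorphone, counted from dose 1, opens as written at 25 + 60 = 85 to 55 + 60 = 115 minutes. With the condition it opens at about 60 + 60 = 120 minutes, later by the same 5 to 35 minutes.
- Ibuprofen as written opens at 25 + 30 = 55 to 55 + 30 = 85 minutes. Used as a bridge it is given at 25 to 55 minutes, so 30 minutes earlier.

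The assumed times were chosen to represent short cases. They show that early re-dosing is possible, not how common it is.

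**The case against.** The strongest objection is that different situations can justify different rules. The operating-room dose goes to an anesthetized patient by the clock, with no pain score, so a time floor is a natural safeguard. The PACU dose goes to a supervised patient who reports pain above 4/10, and the score may be meant as the safeguard. The 1-hour condition also exists only if the interim trigger is met. A reader might infer that the plan forbids a second dose within the hour and so contradicts itself in the PACU. The documents do not support that: the condition is written for the operating-room dose alone. This part of the objection stands.

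It is also fair that dose 1 precedes incision, so surgery, emergence and transfer may use up the hour in many cases, and that spacing may be governed by guidance outside this text, which cannot be checked here. Finally, withholding the study opioid has a cost in a population whose main problem, on the Introduction's account, is uncontrolled postoperative pain.

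None of this supplies a PACU interval. The line is not merely silent: followed literally, it directs the dose as soon as the score exceeds 4/10. If a shorter interval is acceptable for a pain-triggered dose, the plan should state it.

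**Conclusion.** The point holds as a minor patient-safety improvement. As written, a short-case patient can receive a second 30 mcg within an hour of the first, although the plan's only spacing condition for that dose, set for another setting, is longer. Under the assumed short-case times the second dose comes 5 to 35 minutes before the hour. The number of patients affected cannot be computed without case lengths and may be small.

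A reader might go further and infer that early re-dosing biases the comparison of perioperative opioid use. The documents do not show this, and the sample size and planned tests are untouched. Nor do they show that the 1 hour is the pharmacologically correct interval. It is simply the plan's own figure and therefore the obvious default.

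**What to change.** Change the condition on the PACU line to: *If pain > 4/10 and more than 1 hour has passed since the 1st dose*, followed by the existing instruction for the 2nd dose.

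Add a bridge: if pain exceeds 4/10 before the hour is reached, give the existing ibuprofen step first, once only, so that it is not repeated 30 minutes after dose 2. The clinical team should confirm this, including whether it suffices for severe pain. If the team intends a shorter interval for a pain-triggered PACU dose, write that interval in place of the hour.

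Add to the interim rule: any of the first 15 patients with PACU pain above 4/10 before the hour counts as requiring a second dose, whether or not dose 2 is later given. Otherwise the wait itself could lower the 8-of-15 count.

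The cost is a short text change in two places plus clinical agreement on the bridge. The downside is real but small: some short-case patients in pain wait for dose 2, and hydromorphone, timed from dose 2, opens later by the same amount.
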